Liver Fibrosis Evaluation Using Ultrasound Shear Wave Imaging

NCT03637959

March 29, 2019

IRB Minimal Risk Protocol Template

General Study Information

Principal Investigator: [name]

Study Title: Liver Fibrosis Evaluation Using Ultrasound Shear Wave Imaging

Protocol version number and date: March 29, 2019

Purpose

Hypothesis: Liver stiffness measured by Ultrasound Shear Wave Imaging is correlated with liver stiffness measured by MRE (Magnetic Resonance Elastography).

Aims, purpose, or objectives: Liver stiffness measured by MRE can be used for noninvasive liver fibrosis staging. However, MRE is expensive and not widely available. This study will evaluate the efficacy of liver stiffness measured by ultrasound for fibrosis staging, using clinically indicated MRE as the gold standard. A secondary aim is to measure the fat content of liver using ultrasound and to study the correlation of liver fat and fibrosis.

Background (*Include relevant experience, gaps in current knowledge, preliminary data, etc.*):

Liver fibrosis/cirrhosis afflicts hundreds of millions of patients worldwide and 900,000 Americans. Liver biopsy, currently the gold standard for the diagnosis of liver fibrosis, is invasive and may occasionally cause significant complications, which limits the screening of at-risk populations, treatment monitoring, and follow-up. Liver stiffness measured by MRE (Magnetic Resonance Elastography) is used clinically at Mayo for non-invasive liver fibrosis staging. In MRE, small mechanical vibrations are applied at body surface and shear waves (mechanical waves due to vibration perturbation) thus introduced in liver is detected by Magnetic Resonance Imaging and used to calculate the stiffness of liver. However, MRI is expensive and not widely available. In this study, we will evaluate the feasibility of using ultrasound to detect shear waves introduced by small mechanical vibration for liver fibrosis staging. We expect that this new method will have better penetration compared to existing ultrasound elastography techniques, and therefore has more reliable measurements in obese patients. This is an important advantage considering prevalence of obesity in USA.

Subject Information – charts, records, images, or specimens are considered ‘subjects’

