Study on patients and volunteers will take place in the Radiology department using the GE Logiq E9 scanner (FDA approved), GE Logiq E10 (FDA approved), and the Verasonics ultrasound scanner. The first ultrasound scan will be about 10 minutes using the GE Logiq E9 scanner and optionally the GE Logiq E10 scanner to measure the stiffness of liver (used as a benchmark reference in this study). The second ultrasound scan will be about 30 minutes using the Verasonics scanner. In the second scan, multiple miniature mechanical vibrators will be placed on the body surface of rib cage of the subject. An elastic strip (fibric covered neoprene) wrapped around the chest and secured by hook-and-loop will be used to hold the mini-vibrators in contact with body surface. Alternatively, mechanical vibrations are introduced by an audio loudspeaker in contact with the subject's upper torso. Or mechanical vibration will be introduced through a miniature vibrator attached to the ultrasound probe. An experienced sonographer from Mayo will image the liver with an ultrasound transducer. The best intercostal window that shows an area of the hepatic lobe away from the diaphragm and adjacent vessels will be chosen. Repeated stiffness measurements will be made at different locations within the liver parenchyma while the mini-vibrators introduce shear wave in the liver, similar to an MRE examination. The subject will be instructed to briefly hold his/her breath during each measurement. This procedure will take about 30 minutes. The study is non-invasive and imposes no discomfort to the subject. Liver MRE results will be obtained from the medical record of the patient and compared with ultrasound results. Most healthy volunteers will not have liver MRE examination and therefore liver stiffness measured by mechanical vibrations will be compared with those obtained with the GE Logiq E9 scanner. Some healthy volunteers may be offered liver MRE examination so that we can compare the ultrasound and MRE measurements in the healthy cohort. Other clinical information relevant to liver diseases if available, such as results of liver biopsy or liver function tests, will also be obtained from medical records to assist data analysis. If a healthy volunteer were found to have abnormal liver stiffness by MRE performed as part of this research study, we will inform the healthy volunteer, and if requested, to his/her primary care provider. We will not communicate with patients on their MRE results, as their MRE examinations are clinically indicated and they should be aware of their MRE results from their clinical care provider. Reliability of the new ultrasound technology used in this study for liver disease diagnosis is not established yet. Therefore, participants will not be informed of research ultrasound measurement results. Incidental findings in subjects if noted (e.g if splenomegaly, adenopathy, or a mass) will be communicated to the subject, and if requested, to his/her primary care provider.

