
In addition to liver stiffness data, un-processed ultrasound data from conventional B-mode ultrasound imaging will be collected and analyzed offline to estimate the liver fat content. Completely de-identified data may be shared with GE to see if more advanced GE processing can improve the outcome. Correlation of liver stiffness (reflecting fibrosis) and liver fat content (reflecting steatosis) will be analyzed. Information from the patients' medical record about the status of liver disease may be used to help interpreting the results. We may screen potential patient candidates' MRE results to help select patients to enroll for this study, to ensure that we have a relatively uniform distribution of patient population to cover the full spectrum of the disease.

Resources: *Describe the available resources to conduct the research (personnel, time, facilities, mentor commitment, etc.):*

This project will be funded by a NIH R01 grant. [name] (GI) and [name] (Radiology) are co-investigator of this project. We have commitments from all participating personnel and their efforts will be funded by the R01 grant.

Check all that apply. If none apply, leave blank:

This is a multisite study involving Mayo Clinic and non-Mayo Clinic sites.

When checked, describe the research procedures/activities being conducted **only** at Mayo Clinic:

Mayo Clinic staff will be engaged in research activity at a non-Mayo Clinic site. *When checked, provide the location and a detailed description of the Mayo Clinic research staff involvement.*

This study is to establish and/or maintain an ongoing database or registry for research purposes only.

The research involves contact or interaction with subjects, for example, surveys, questionnaires, observation, blood draw.

The study involves audiotaping or videotaping

Blood Collection

If this study involves prospective blood collection by finger, heel, ear stick or venipuncture, complete the following:

From healthy, non pregnant, adult subjects who weigh at least 110 pounds. For a minimal risk application, the amount of blood drawn from these subjects may not exceed 550ml in an 8 week period and collection may not occur more frequently than 2 times per week.

Volume per blood draw: _____ ml

Frequency of blood draw (e.g. single draw, time(s) per week, per year, etc.) _____

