Detailed data analysis plan can be found in page 66-68 of the NIH application, which is attached to Section 47 (Supporting Documents) of this IRB application.

Endpoints

Primary: We study 325 subjects with successful MRE and ultrasound measurements.

Secondary: Some patients will have failed MRE or ultrasound measurements due to technical difficulties. We therefore will continue recruiting up to 400 subjects until we reach the primary end point.

Data Analysis Plan

Intraclass correlation coefficients (ICC) will be calculated from random effects models to evaluate the inter-sonographer agreement. For these models, subject and sonographer will both be included as random effects. The within subject variance components from the model will be used to obtain an estimate of the overall measurement variance for REVUE. In addition to the overall analysis, we will compare repeatability and reproducibility measures across subgroups defined according to subject BMI (<30 and ≥ 30) and perform supplemental analyses separately for each BMI category as appropriate. In all cases, findings will be presented using point estimates and 95% confidence intervals.

The primary objective is to demonstrate whether REVUE is an effective alternative to MRE for distinguishing patients with minimal fibrosis (MRE ≤ 2.9 kPa) and advanced fibrosis (MRE ≥ 5.0 kPa). To accomplish this objective, ROC curve analyses will be performed using logistic regression for these MRE cut points. Separate analyses will be performed to assess the performance of both REVUE and Aixplorer®. The results of these analyses will be summarized using the point estimate and 95% confidence interval for the area under the ROC curve (AUROC). In addition, we will compare the AUROC between ultrasound methods using the approach described by DeLong. Secondary analyses will be performed using Pearson product-moment correlation and linear regression to evaluate the association of REVUE and Aixplorer® measurements with MRE. The correlation coefficients obtained from these analyses will be summarized and compared (REVUE vs. Aixplorer®) using the method described in. To supplement the overall findings, we will repeat the analyses according to BMI (all BMI vs. $BMI \geq 30$) and, if appropriate, according to disease (chronic viral hepatitis and alcoholic/nonalcoholic fatty liver disease). In all cases, two-tailed p-values ≤ 0.05 will be considered statistically significant.

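### The supplementary accuracy analyses pair all BMI with BMI ≥30, so the visible plan gives no BMI <30 accuracy result and cannot show whether any REVUE advantage is specific to obese patients

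*Combined protocol and SAP*

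**What the plan says.** The Data Analysis Plan under Endpoints handles BMI in two ways.

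- **Repeatability and reproducibility.** Measures are compared across "subgroups defined according to subject BMI (<30 and ≥ 30"), two groups that do not overlap. Separate supplemental analyses for each category follow where appropriate.
- **Accuracy against MRE.** AUROCs are estimated for REVUE and Aixplorer at the MRE cut points of 2.9 and 5.0 kPa, and "we will compare the AUROC between ultrasound methods using the approach described by DeLong". Pearson correlations with MRE are also compared between methods. Then: "To supplement the overall findings, we will repeat the analyses according to BMI (all BMI vs" BMI ≥30).

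The Background explains why BMI matters: the expectation is that "this new method will have better penetration compared to existing ultrasound elastography techniques, and therefore has more reliable measurements in obese patients".

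Two limits on what can be read from the text:

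- The Statistical Considerations section refers elsewhere for the full plan: "Detailed data analysis plan can be found in page 66-68 of the NIH application". Those pages are not in the document.
- The comparator named in the analysis plan, Aixplorer, is not among the devices listed in Methods, where scanning is done "using the GE Logiq E9 scanner (FDA approved), GE Logiq E10 (FDA approved), and the Verasonics ultrasound scanner". The point applies to whichever ultrasound comparator is actually acquired.

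**The concern.** A split by BMI would normally give one result for obese and one for non-obese patients. Here the two sets are nested. Everyone with BMI ≥30 is also in the all-BMI set, and the all-BMI result is already the overall analysis. The repeat therefore adds one new result, and BMI <30 is never reported for accuracy.

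This affects interpretation. Suppose REVUE has a higher AUROC than the comparator at BMI ≥30. That could be because the comparator loses signal in obese patients and REVUE does not, which is the penetration argument. It could also be because REVUE is the better device at every BMI. Only the BMI <30 result separates these two, and the visible text does not ask for it.

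**Working it through.** **1. The plan's own figure.** The Power Statement builds the total as 60 (pilot) + 45 (Aim 2) + 220 (Aim 3) = 325, which reproduces. The point does not depend on it. The documents give no obese share, expected AUROC or effect size, so every magnitude below rests on stated assumptions.

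**2. The two BMI rules side by side.**

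| Analysis | BMI sets | Relation | BMI <30 reported? |
|---|---|---|---|
| Repeatability, reproducibility | <30 and ≥30 | disjoint | yes |
| AUROC, DeLong, correlation | all and ≥30 | nested | no |

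No interaction term or between-strata contrast is stated for the accuracy analyses.

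**3. Can the BMI <30 AUROC be derived from the two planned results?** An AUROC is an average over pairs of one patient above and one below the cut point. With a share *f* of obese patients on each side of the cut point:

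AUC(all) = f² × AUC(obese) + 2f(1−f) × AUC(cross) + (1−f)² × AUC(non-obese)

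The cross term covers pairs with one obese and one non-obese patient, and neither planned output reports it. For assumed f = 0.2 / 0.4 / 0.6 it makes up 2f(1−f) = 32% / 48% / 48% of all pairs. For illustration take f = 0.5, AUC(all) = 0.90 and AUC(obese) = 0.85:

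AUC(non-obese) = (0.90 − 0.25 × 0.85 − 0.5 × AUC(cross)) / 0.25

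- cross 0.88: (0.90 − 0.2125 − 0.44) / 0.25 = 0.99
- cross 0.90: (0.90 − 0.2125 − 0.45) / 0.25 = 0.95
- cross 0.95: (0.90 − 0.2125 − 0.475) / 0.25 = 0.85

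The same two planned outputs fit a BMI <30 AUROC well above the obese one or equal to it. The missing result has to be estimated directly.

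**4. How precise would the added results be?** Simulation with all inputs assumed:

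- MRE uniform on 1.5–8 kPa, following the stated wish for a "relatively uniform distribution of patient population to cover the full spectrum of the disease"
- independent normal errors
- REVUE error SD 0.7 kPa in both strata
- comparator SD 0.7 kPa in non-obese patients and 0.7, 1.0, 1.4 or 2.1 kPa in obese patients
- obese share 0.2–0.6, and 1,500 runs per setting

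No visible text ties 220 to the ROC analysis. The endpoint reads "Primary: We study 325 subjects with successful MRE and ultrasound measurements". Both numbers are therefore shown. The 95% half-width is 1.96 × the SD over runs.

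| AUROC result | N = 220, cut 5.0 | N = 220, cut 2.9 | N = 325, cut 5.0 | N = 325, cut 2.9 |
|---|---|---|---|---|
| Paired difference, BMI <30 | 0.020–0.030 | 0.028–0.041 | 0.016–0.025 | 0.023–0.033 |
| Between-strata difference | 0.038–0.120 | 0.050–0.149 | 0.030–0.096 | 0.041–0.118 |

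For comparison, at obese share 0.4 and cut 5.0, comparator SDs of 1.0 / 1.4 / 2.1 kPa in obese patients give true between-strata differences of 0.023 / 0.064 / 0.137. The BMI <30 result is reasonably precise; the contrast often is not.

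A second model points the same way. It assumes N = 220, obese share 30–50%, 20–30% of patients above the cut, AUROC 0.95 throughout except 0.85 for the comparator in obese patients, and within-patient correlation 0.6. A true contrast of 0.10 then has SE 0.041–0.056 and power of about 41–71% at two-sided 5%.

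**5. Counts.** Under the uniform MRE assumption, (2.9 − 1.5)/6.5 = 21.5% of patients lie at or below 2.9 kPa and (8 − 5)/6.5 = 46.2% at or above 5.0 kPa. With N = 220 and f = 0.4, the 88 obese patients include about 19 and 41 of these, and the 132 non-obese about 28 and 61. Small cells are possible, so the counts should be reported.

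**The case against.** **The obesity question is already answered.** The Background speaks of obese patients, and the paired comparison at BMI ≥30 addresses them directly. This stands. A reader might infer that the plan says nothing valid about obese patients, but the text does not support that. No document states a BMI-interaction objective either. That the advantage should be larger in obese patients is an inference from the penetration argument.

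**Reliability is already compared in disjoint groups.** This is true for REVUE's repeatability and reproducibility. The clause on separate analyses for each BMI category belongs to that paragraph and is conditional, while the accuracy paragraph sets its own, different BMI sets. It does not supply a BMI <30 AUROC.

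**Nesting biases nothing.** A reader might infer that the obesity effect will be reported in diluted form, because an obese-minus-all difference is smaller than an obese-minus-non-obese one. The plan specifies no such subtraction, so dilution is not a harm done by any planned output.

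**The detailed plan may cover it.** This is possible and cannot be checked, so the point cannot be read as a claim about the whole plan.

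**The contrast is weak evidence in any case.** This largely stands. It is imprecise. The Exclusion Criteria also remove subjects with unreliable ultrasound or MRE measurements, and the Endpoints section continues recruitment up to 400 until 325 succeed. If poor penetration makes scans fail in obese patients, those patients leave the accuracy set and the contrast may understate the effect. Stratum AUROCs also depend on each stratum's MRE distribution. These are reasons to report counts and exclusions and to keep the contrast descriptive. They do not argue for leaving out the BMI <30 result.

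**Conclusion.** The point holds as a minor gap in a supplementary analysis. The primary analysis is unaffected, the BMI ≥30 comparison is valid, and no planned output is biased. The visible plan provides no BMI <30 accuracy result, so it cannot show whether any REVUE advantage is specific to obese patients or general, and the missing AUROC cannot be recovered from what is planned.

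This conclusion rests on the text alone. The numbers only illustrate size: under the assumed inputs the BMI <30 paired AUROC difference would have a 95% half-width of about 0.02–0.04, and the between-strata difference about 0.04–0.15 with 220 patients or 0.03–0.12 with 325. Confidence is medium because the referenced grant pages may already specify the analysis.

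**What to change.** Keep the overall analysis. In the accuracy paragraph, replace the all-BMI and BMI ≥30 pairing with BMI <30 and BMI ≥30, matching the repeatability paragraph. In each stratum report:

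- the paired REVUE-minus-comparator differences in AUROC and in correlation, with 95% CIs;
- the number of patients on each side of each MRE cut point;
- the number excluded for failed or unreliable ultrasound or MRE measurements.

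Give the between-strata difference with its 95% CI, from two independent DeLong differences or a bootstrap, labelled as descriptive. If pages 66–68 of the grant application already specify this, align the wording here with them.

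The cost is one or two lines of plan text and a little more analysis. BMI <30 patients are already in the all-BMI set, so no patients or scans are added beyond the comparator measurements that the overall comparison already needs. The drawback is one more imprecise estimate, which may understate a penetration effect because failed scans are excluded and replaced.
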